Summary analyses for this study will be performed periodically to generate safety and effectiveness data for regulatory submissions and for review by the Data Safety Monitoring Board (DSMB). Efficacy measures reported in the parent AV-101-002 study will also be collected in the LTE but only for subjects being treated with the open-label optimal AV-101 dose once it is identified. These efficacy measures will be labeled effectiveness measures for LTE reporting.

Safety and effectiveness data will be summarized by AV-101 treatment groups and all subjects combined at cumulative 24-week intervals. Levels in longitudinal continuous, categorical, and time-to-events data will be presented by time-intervals. LTE intervals will be divided into before and after optimal dose treatment. Continuous data will be summarized using the following descriptive statistics: number of observations, mean, standard deviation, standard error, median, minimum, and maximum. Categorical data will be summarized using frequencies and percentages. Changes from baseline will be calculated as the later value minus the baseline value. Baseline will be defined for all endpoints as the time of starting treatment with AV-101 in the parent study (AV-101-002) or baseline LTE. Baseline for subjects previously randomized to placebo will have their baseline defined at Week 24 of the parent study.

Trends or patterns over time in safety and effectiveness measures will be presented graphically, and in repeated measures models applicable to categorical or continuous data. Time-to-event analysis will be performed using Kaplan-Meier procedures as well as a time-to-event model with time-independent and time-varying covariates.

Study Endpoints

- Safety and tolerability of AV-101
- Survival
- Change from baseline in the 6MWD
- Change from baseline in NT-proBNP
- Time to Clinical Worsening events
- Achievement of the multi-component improvement parameters
 - Percent of subjects who achieve the multi-component parameters by visit
 - Time to achieving the multi-component improvement parameters
- Change in WHO Functional Class status
- Change from baseline in REVEAL Lite 2.0 risk score
- Change from baseline in QoL (emPHasis-10) Questionnaire score
- Change from baseline in Transthoracic Echo parameters of right ventricular (RV) function
- Change from baseline in hemodynamics (in subjects who have RHC measures)

Clinical Worsening Events will be defined as:

- Death (all causes)

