6.1 Screening/Baseline Visit

The appropriate baseline assessments for the LTE ([Table 1 Schedule of Assessments](#)) will be collected at the end of study visit (Week 24) for AV-101-002. Depending on outcome for analysis, baseline values reported during the parent trial may be used especially among subjects randomized to active treatment groups. Following Day 1 in the LTE, all subjects will have a telephone visit at Week 1 (7 days) for safety follow up.

Safety

- Review prior (within the past 30 days) and current concomitant medications and therapies
- Record AEs

Randomization

Subjects who were on placebo and entering the LTE from the Phase 2b and Intermediate Parts of Study AV-101-002 will be centrally randomized via an IWRS.

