6.6.5 Clinical Worsening

Clinical worsening events will be defined as:

- Death (all causes)

- Hospitalization for worsening PAH
- Initiation of parenteral prostanoids
- $\geq 15\%$ decline from baseline in 6MWD accompanied with continued or worsening WHO FC III or IV symptoms. The decline in 6MWD must be confirmed with a repeat test on a different day within 2 weeks. (Baseline is defined by the randomization visit in Study AV-101-002 for those on AV-101 and the Week 24 visit for those on placebo in Study AV-101-002).

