- 4) Levels and trends in LTE safety and effectiveness after 24 weeks of optimal dose treatment in each of the four treatment groups will be reported.

Other comparisons will be outlined in the Statistical Analysis Plan.

The association of LTE AV-101 treatment groups with levels and trends in LTE safety will be explored with a continuous AV-101 treatment exposure based on average weekly dose intensity. Planned weekly dose intensity during the parent trial ranges from zero among those who only received placebo treatment, 140 mg/week among those randomized to 10 mg per dose BID, 490 mg/week among those randomized to 35 mg per dose BID and 980 mg/week among those randomized to 70 mg per dose BID. With dose titration, early treatment discontinuation, or missed doses, average dose intensity per week will be calculated by summing up AV-101 with the cumulative sum divided by the duration of treatment in weeks.

Safety and effectiveness endpoints collected while subjects are participating in the parent study will serve as the benchmark for safety and effectiveness endpoints collected during the LTE study. LTE levels of safety and effectiveness endpoints will be presented by LTE treatment groups and LTE visits intervals disaggregated by visits prior to or after subjects are dosed with the optimal dose. These safety and effectiveness levels will be presented using descriptive statistics applicable to continuous or categorical data. Trends or patterns over time in a select set of safety and effectiveness measures will be presented graphically. Continuous data will be summarized using the following descriptive statistics: number of observations, mean, standard deviation, standard error, median, minimum, and maximum. Categorical data will be summarized using frequencies and percentages.

Changes from baseline will be calculated as the later value minus the baseline value. Baseline will be defined for specific endpoints as the time prior to starting active treatment with AV-101 in either the LTE or the parent study. Baseline values for subjects will consist of the baseline values during the parent trial among subjects in the always active treatment groups (optimal dose [Group 1] or non-optimal dose [Group 2]). For subjects who are initially assigned to placebo in the parent

trial, baseline values consist of either Week 24 parent trial values or baseline LTE prior to re-randomization to active treatment.

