8.4 Baseline and Demographics and Subject Study Disposition

With exception of the delayed-start analysis, for both the efficacy and safety analyses, baseline will be defined as the time prior to starting active treatment with AV-101 in either the LTE or the parent study. For Groups 1 and 2, since the subjects start receiving active treatment in the parent study, the baseline will be the values prior to first dose during the parent trial. For Groups 3 and 4, the subjects receive placebo in the parent trial and then receive active treatment in the LTE study, thus, the baseline will be the values prior to the first dose in LTE study.

Demographics and baseline data, medical and surgical history will be summarized using the screened analysis set. These demographics and baseline data will be presented by the LTE treatment groups as described in [Section 8.1](#).

Demographic and baseline data will be summarized using summary statistics of mean, standard deviation, median, lower quartile, upper quartile, min and max for continuous variables and number and percentage of subjects in each category.

Subject treatment status and study participation status will be reported for the safety analysis set. Subjects who completed all LTE assessments and early treatment discontinuation and withdrawal from the study including reasons for treatment or study discontinuation will be reported by LTE treatment groups.

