Visits within a subject form a cluster. Estimated proportions by treatment group and visit will be reported. For Week 24 after optimal dose treatment, the log of odds and proportions of subjects who maintain or improve WHO FC and their 95%CI will be reported by treatment groups. Odd ratios (OR) and 95%CI for subjects always on optimal dose (Group 1) relative to those subjects on always on placebo (Group 4) will be reported. OR and 95%CI among subjects always on optimal dose (Group 1) relative to those of subjects on placebo and then active treatment (Group 3) and OR and 95%CI among subjects always on optimal dose (Group 1) relative to those of subjects on non-optimal dose (Group 2) will also be reported.

4) Time to Clinical Worsening

Time to clinical worsening while in the parent trial and LTE will be based on the first occurrence of any of the following events for each subject.

- Death
- Initiation of parenteral prostanoids
- Hospitalization for worsening PAH
- $\geq 15\%$ decline from baseline in 6MWD and accompanied with progression to or continued WHO FC III or IV symptoms

A subject is evaluated for experiencing any of the above components of clinical worsening throughout the parent trial and LTE study period. Time to clinical worsening is the number of days between the earliest occurrence of the clinical worsening component and the date of the first dose in the parent trial. With treatment groups that change over time intervals, event and censoring will be defined within each time interval. A subject who does not experience any of the clinical worsening component throughout a treatment period/interval is censored and is assigned time to worsening status by the end of the interval. Subjects who are lost to follow-up are typically considered censored. Supplemental analyses will be performed where subjects with an unknown clinical worsening event will be considered to

experience the event and the time to clinical worsening status is the last contact with the subject.

The probability of clinical worsening every 24 weeks after the first dose in the parent trial throughout the LTE will be reported, descriptively as well as based on a Cox model for time to clinical worsening while holding covariates at their means.

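### Clinical worsening is timed from first parent dose in every group, but as written the walk reference for parent-placebo subjects is Week 24, so the event definition is unequal in the planned group comparisons

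*Combined protocol and SAP*

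**What the plan says.** **Clock.** Section 8.5.2 item 4 counts days from the first parent dose to the first component event. It evaluates every component over the parent trial and the LTE, and excepts no group. It plans event probabilities every 24 weeks on that clock, a Cox model with hazard ratios for Group 1 against Groups 4, 3 and 2, and Kaplan-Meier curves by parent arm.

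**Walk component in that section.** A fall of at least 15%, worded as "decline from baseline in 6MWD and accompanied with progression to or continued WHO FC III or IV symptoms". The section does not say which baseline is meant.

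**Which baseline.** The endpoint's own definition, in the synopsis, Section 2.2 and Section 6.6.5, reads: "Baseline is defined by the randomization visit in Study AV-101-002 for those on AV-101 and the Week 24 visit for those on placebo". The general rules agree for parent-placebo subjects:

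- Synopsis, Statistical Methods: "Baseline will be defined for all endpoints as the time of starting treatment with AV-101 in the parent study (AV-101-002) or baseline LTE", followed by "Baseline for subjects previously randomized to placebo will have their baseline defined at Week 24 of the parent study".
- Section 8.1, for subjects first assigned to placebo: "baseline values consist of either Week 24 parent trial values or baseline LTE prior to re-randomization to active treatment".
- Section 8.4: "With exception of the delayed-start analysis, for both the efficacy and safety analyses, baseline will be defined as the time prior to starting" active treatment; for Groups 3 and 4, "thus, the baseline will be the values prior to the first dose in LTE study". The delayed-start analysis is the only exception.

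**The one looser sentence.** Section 6.1: "Depending on outcome for analysis, baseline values reported during the parent trial may be used especially among subjects randomized to active treatment groups".

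**The concern.** A walk taken in Weeks 0 to 24 cannot be a decline from a value measured at Week 24. On this clock, Groups 1 and 2 have a usable walk reference from the start. Groups 3 and 4 have none for the first 24 weeks, and afterwards they are judged against a post-placebo value while Groups 1 and 2 keep a pre-treatment value.

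At stake are the Group 1 versus 4 and Group 1 versus 3 hazard ratios, the 24-weekly probabilities and the Kaplan-Meier curves by parent arm, all on a first-tier effectiveness endpoint. Group 1 versus Group 2 is not affected, because both use the randomization visit. The other components do not depend on a walk reference: hospitalization for PAH and start of parenteral prostanoids count in all groups throughout. Death cannot fall in Weeks 0 to 24 in any group, because Section 4.1 requires completion of the parent study.

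**Working it through.** The documents give no event rate, event count or power for this endpoint, so there is no planned figure to reproduce. The finding comes from setting the sections side by side. The numbers only illustrate its size.

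**Step 1. Time in which a walk event can be scored, as written**

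| | Groups 1-2 | Groups 3-4 |
|---|---|---|
| Clock starts (8.5.2 item 4) | first parent dose | first parent dose |
| 6MWD reference (6.6.5, 8.4) | parent randomization | parent Week 24 / before first LTE dose |
| Scorable weeks in Weeks 0-24 | 24 | 0 |
| First scheduled walk that can count | first post-randomization walk | LTE Week 4 (Table 1), about Week 24 + 4 = 28 |

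**Step 2. The early gap alone, with no drug effect**

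Assumptions: walk share s of the hazard 20% to 60%; annual event risk p 15% to 30%; equal group sizes; constant hazard L = -ln(1 - p)/52 per week. Group 1 has hazard L throughout. Group 4 has (1 - s)L in Weeks 0-24, then L.

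Hand check by average hazard: over T weeks Group 4 averages L(1 - 24s/T), so the ratio is about 1/(1 - 24s/T).

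- T = 48: 1/(1 - 0.10) = 1.11 to 1/(1 - 0.30) = 1.43
- T = 96: 1/(1 - 0.05) = 1.05 to 1/(1 - 0.15) = 1.18
- T = 144: 1/(1 - 0.033) = 1.03 to 1/(1 - 0.10) = 1.11

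The Cox estimate weights early time more, because subjects leave the risk set after an event. The large-sample value solves, for b, the integral over (0, T) of S1h1 - (S1h1 + S4h4) x S1e^b/(S1e^b + S4) = 0, where h and S are the hazard and event-free probability in each group. Range of e^b over s and p:

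| Follow-up | Base case | Weeks 0-24 hazards halved in both groups |
|---|---|---|
| 48 weeks | 1.12-1.47 | 1.07-1.27 |
| 96 weeks | 1.06-1.23 | 1.03-1.12 |
| 144 weeks | 1.04-1.17 | 1.02-1.09 |

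The last column allows for the selection of parent completers, who may have had fewer early events.

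**Step 3. The Week 24 reset**

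Take 400 m at randomization. A Group 1 subject has a walk event at 0.85 x 400 = 340 m. For a parent-placebo subject the threshold depends on the Week 24 walk:

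- 340 m at Week 24: 0.85 x 340 = 289 m, which is 1 - 289/400 = 27.75% below randomization. Events are harder to reach than in Group 1.
- 440 m at Week 24: 0.85 x 440 = 374 m, which is 1 - 374/400 = 6.5% below randomization. Events are easier to reach.

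**Step 4. Both features together, with no drug effect**

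A threshold-based simulation shows that the sign can change. Assumptions: mean 380 m; slope -0.1 m/week (SD 0.35); test noise SD 15-25 m; other events at 60% of the hazard for a 15% annual risk; walks at Weeks 4, 12, 24, 28, 36 and 48, then every 12 weeks; functional class and confirmation rules left out. At 96 weeks the Group 1 versus 4 hazard ratio was about 1.25 to 1.27 with no shared change in walk distance, 0.92 to 0.93 with a gain of 15 m in all arms by Week 12, and 0.71 to 0.78 with 30 m. The values move with the assumptions. What matters is that they fall on both sides of 1.

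**The case against.** **The parent baseline may have been meant.** Section 6.1 allows parent-trial baselines depending on the outcome. Section 6.6.5 sits among the LTE assessments, and Table 1 collects clinical worsening only from LTE Week 1. Section 8 defers details to a SAP, and the scoring of parent-period worsening belongs to a protocol not supplied here. This stands as a limit: if the randomization reference is used for Groups 3 and 4 on this clock, no bias arises. But Section 6.1 is permissive and aimed mainly at active arms, while every section that defines the baseline for parent-placebo subjects says Week 24 or before first LTE dose.

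**Interval rules may repair it.** Section 8.5.2 item 4 defines events and censoring within intervals and uses time-varying dose groups. These classify exposure; they supply no walk reference for the placebo interval.

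**A reader might infer that the rule only works against AV-101 and so could not create a false benefit.** The documents do not support this. It holds for the early gap alone. The Week 24 reset acts on the same estimates and can favour Group 1 if walk distance rises in all arms during the parent study.

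**A reader might also infer a larger distortion in the dose-intensity Cox models of Section 8.1.** No figure is given here. That section defines average dose intensity as the cumulative amount over treatment duration, so former-placebo subjects could keep lower values after switching. It is also unclear whether the Group 4 label in the hazard ratio list means a placebo dose level.

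**The study's main aim is safety.** True, and this limits the weight of the point. The comparisons are nevertheless planned on a first-tier endpoint.

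**Conclusion.** The point holds as a contradiction between clock and reference, read as written. It gives unequal event definitions in planned comparisons of Group 1 with Groups 4 and 3, and is confined to the walk component of one endpoint. The text itself does not establish bias, because Section 6.1 leaves another reading open.

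The early gap alone would move a null hazard ratio to the Step 2 ranges, and less if completers had few early events. Those ranges rest on assumed walk shares and annual risks, and must not be read as the expected total bias. With the reset included, the net direction is undetermined and a false benefit is possible. The contradiction itself depends on none of these assumptions. It should be fixed; confidence is medium, because the intended reading cannot be seen from these documents.

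**What to change.** 1. For the analysis timed from first parent dose, use the parent randomization 6MWD as the walk reference in all four groups, and add this analysis to the exception in Section 8.4.
2. Use the Week 24 reference only in a separate analysis of Groups 3 and 4 timed from first LTE dose.
3. Reconcile the synopsis (Statistical Methods and Clinical Worsening), Sections 2.2, 6.6.5, 8.1, 8.4 and 8.5.2 item 4, and the SAP, by stating which reference belongs to which clock.
4. Say whether the repeat walk within 2 weeks, required in the synopsis and Sections 2.2 and 6.6.5, also applies in Section 8.5.2 item 4, which does not mention it. Apply one rule to all four groups.

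With a common reference, the null hazard ratio in the Step 2 illustration is 1.00 by construction.

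**Cost.** Wording only. The randomization visit is already the reference visit for Groups 1 and 2, so no new assessment is needed. The downside is that some placebo declines will now be dated in the parent period and may lack a confirming walk, because the documents do not say whether repeat walks were done in AV-101-002. The choice is best made before programming: under Section 3.1 the LTE is no longer blinded once the optimal dose is selected.

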Given the demonstrated clinical efficacy of oral imatinib in PAH, Aerovate is developing a dry powder inhaled imatinib, AV-101, to target the delivery of imatinib to the diseased organ, the lungs. Inhaled administration of AV-101 is expected to provide rapid local exposure of respiratory tissue to imatinib with a lower dose and lower systemic exposure compared to Gleevec® oral tablets. Aerovate expects that inhaled AV-101 administration will result in a more favorable benefit/risk profile than that observed with oral Gleevec administration. Therefore, subjects who successfully complete the 24-week placebo-controlled trial (AV-101-002) will be offered the opportunity to continue into this long-term extension (LTE) study.

Overview and Objectives:

The primary objective of the study is to establish the long-term safety of AV-101. The long-term effects of AV-101 on efficacy measures (e.g., 6MWD, NT-proBNP, cardiac echo) will also be assessed.

Overall Design:

Study AV-101-003 is a long-term extension (LTE) follow up study where recruitment of subjects will continue as the parent study (AV-101-002) progresses from Phase 2b to Phase 3. Subjects who were on placebo in Phase 2b and the Intermediate Part of the study who enroll in the LTE study will be re-randomized to one of the 3 active AV-101 doses until such time as the optimal dose has been selected. Once the optimal dose of AV-101 has been selected, all subjects will be transitioned

to the optimal dose while they continue in the LTE, and subjects completing the Intermediate Part or parent study Phase 3 will enroll into the LTE study at the optimal dose.

Subjects enrolling into the LTE study will be closely followed for the first 24 weeks given that those who transition from placebo will be receiving AV-101 for the first time (See Schedule of Assessments [Table 1](#)). Study visits will be every 3 months after completing the first 24-week period. Investigators and subjects will remain blinded to the randomization in the parent study until the optimal dose has been selected for the Phase 3 part in AV-101-002.

Number of Study Sites: Approximately 140 sites globally

[figure not shown]
Number of Subjects: Up to approximately 462 subjects

Involvement of Special Committee(s): There will be an independent data safety monitoring board (DSMB) to oversee the safety and welfare of study subjects ([Section 3.3](#)).

[figure not shown]
Figure 1 Study Design of AV-101-003

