3.1 Overall Design

Figure 1: Study Design of Study AV-101-003

For Subjects Entering the LTE from the Phase 2b and Intermediate Parts of AV-101-002

For Subjects Entering the LTE from the Phase 3 Part of AV-101-002

- A. Screening/Baseline Visit and procedures for the LTE will be conducted at the Week 24 Visit for AV-101-002.
- B. Once the optimal dose is selected for the parent Phase 3 Part of AV-101-002, subjects who enter the LTE from the Phase 2b Part and the Intermediate Part of AV-101-002 will be transitioned to the optimal dose.
- C. Once the AV-101 optimal dose has been selected, the LTE will no longer be blinded. Subjects enrolled during the Intermediate Part of AV-101-002 that enter the LTE study after the optimal dose is selected will be assigned to that dose upon completion of the Week 24 Visit for AV-101-002.

The doses administered in the Phase 2b and Intermediate parts of Study AV-101-002 are 10 mg, 35 mg, and 70 mg BID. In the LTE study subjects will continue on these doses and placebo subjects will be re-randomized to one of these active doses until such time as the optimal dose has been selected from the Phase 2b data based upon efficacy, safety, and tolerability. Once the optimal dose has been selected subjects in the LTE will be transitioned to the optimal dose. Subjects enrolled during the Intermediate Part of AV-101-002 that enter the LTE study after the optimal dose is selected will be assigned to that dose upon completion of the Week 24 Visit for AV-101-002. Subjects on the optimal dose or placebo in the Phase 3 Part of AV-101-002 will continue in the LTE at the optimal dose.

The schedule of activities and visit frequency will be similar to the parent study (AV-101-002) for the first 24 weeks of the LTE ([Table 1](#)). Thereafter, the interval between study visits will be increased to every 3 months. In the LTE study the quality-of-life instrument used will be the emPHasis-10 questionnaire. Investigators are encouraged to collect RHC hemodynamics in subjects who have in their opinion normalization or near normalization of hemodynamics on the transthoracic echo.

In a small cohort of subjects treated with oral imatinib for PAH, a responder analysis showed that the treatment duration for a complete hemodynamic response was approximately 3 years ([Speich, 2015](#)). Therefore, the LTE study will continue until 31 December 2025 or until the Sponsor stops the study.

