The Week 24 end of study visit of the parent study (AV-101-002) also represents the baseline visit for the LTE study (AV-101-003). The following assessments will be conducted/collected during the baseline visit of the LTE and at selected time points specified in the Schedule of Assessments (Table 1). Additional procedures deemed necessary as part of standard of care may be performed at the discretion of the Investigator. All missed visits and any performed procedures that are not protocol-specified activities must be documented in the subject's medical record and the appropriate eCRF. General considerations for study visits include, but are not limited to the following:

- No protocol waivers or exemptions are allowed.
- Immediate safety concerns should be discussed with the CRO Medical Monitor immediately upon occurrence or awareness to determine if the subject should continue or discontinue study drug.
- Adherence to the study design requirements, including those specified in the Schedule of Assessments, is essential and required for study conduct (see Section 6.7.1 for COVID-19 considerations).
- The Investigator will obtain written informed consent before the end of study visit for study AV-101-002 and as specified in Section 9.1.3 (Informed Consent Process). Upon the subject's agreement, their primary health care provider should be informed about the subject's enrollment in the study.
- Order of Procedures:
 - Health-related QoL assessments should be performed prior to all other study procedures.
 - Vital signs should be collected prior to blood draws. Blood samples for NT-proBNP levels should be collected prior to the 6MWT.
 - All other study assessments should also be performed, according to the Schedule of Assessments (Table 1).
- **Unscheduled visits:** may occur at any time during the study with the assessments to be performed according to the Investigator's judgment. Unscheduled visits may also be necessary for study drug dispensing following temporary withdrawal as described in Sections 6.7 and 7.7.

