8.3 Treatment Exposure, Estimated Number of Subjects in Group Comparisons of Interest

LTE-eligible subjects from the Phase 2b and Phase 3 parts of the parent study will complete 24-weeks of treatment as part of that study, additional weeks of treatment under the same active treatment arms as they enter LTE and until they start optimal dosing once this dose is identified at the end of Phase 2b.

LTE-eligible subjects from the Phase 2b and Intermediate Parts of the parent study who are randomized to placebo will be re-randomized in a blinded manner to any of the active treatment dose groups at LTE entry and prior to being treated with the optimal dose at the end of Phase 2b. Depending on the timing of their enrollment and initial treatment in the Intermediate part of the study, treatment duration under the parent study will be at least 24 weeks prior to being treated

with the optimal dose at the end of Phase 3. The actual duration of treatment during the parent study, during the waiting period for the optimal dose and during the LTE, will be reported.

LTE subjects will be treated at different dose levels prior to the optimal dose being identified. In addition, duration of treatment under the parent dose among those in the Phase 2b and Intermediate Parts may vary before the optimal dose is identified at the end of Phase 2b. Thus time-varying treatment exposure is a key characteristic of the combined parent and LTE trials and will be considered in describing levels and trends in safety and effectiveness endpoints recorded during the LTE trial.

The actual number of subjects by LTE treatment groups will be reported. Summary descriptive statistics will be reported for dose intensity and relative dose intensity by LTE treatment groups. Patterns of continuous dose intensity will be described by fitting a polynomial regression with dose intensity as a response variable and weeks in the study as polynomial splines. In addition, levels and patterns of dose intensity (and relative dose intensity) over LTE time intervals will be described.

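### While sites are blinded, the 15% walk-distance trigger for clinical worsening rests on a baseline set by parent allocation, so some 2-week confirmatory walks can be missed

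*Combined protocol and SAP*

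**What the plan says.** The synopsis, Section 2.2 and Section 6.6.5 give the same 6MWD component of clinical worsening: at least a 15% "decline from baseline in 6MWD accompanied with continued or worsening WHO FC III or IV symptoms". All three add that "The decline in 6MWD must be confirmed with a repeat test on a different day within 2 weeks", and that "Baseline is defined by the randomization visit in Study AV-101-002 for those on AV-101 and the Week 24 visit for those on placebo".

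On blinding, the synopsis (Overall Design) says "Investigators and subjects will remain blinded to the randomization in the parent study until the optimal dose has been selected". Section 8.3 says that parent placebo subjects "will be re-randomized in a blinded manner to any of the active treatment dose groups at LTE entry", so entry to the extension does not reveal who had been on placebo. Section 3.1 ends the blind: "Once the AV-101 optimal dose has been selected, the LTE will no longer be blinded". For Phase 3, the same section says "Subjects on the optimal dose or placebo in the Phase 3 Part of AV-101-002 will continue in the LTE at the optimal dose". It does not say when those subjects' parent arm is disclosed to the site.

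Table 1 schedules the 6MWT at baseline, Weeks 4, 12 and 24, and every 12 weeks after that. It has clinical worsening assessed at most post-baseline contacts, and it has no row for a confirmatory walk. Section 6 treats the parent Week 24 visit as the extension's baseline visit.

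In Section 8.5.2, item 4 (Time to Clinical Worsening) lists the same 15% component but mentions neither a repeat walk nor which baseline applies.

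**The concern.** The site has to order the repeat walk, and it has 2 weeks to do so. The rule that says whether a repeat is due needs the subject's parent arm, which the site is not allowed to know during the blinded period. The documents give no default baseline, no central flag and no instruction to check both values.

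Time to clinical worsening is a first-tier endpoint in Section 8.5.2, with hazard ratios for Group 1 against Groups 4, 3 and 2. If sites settle on one reference value for everyone, the untriggered repeats fall on one side of the parent active/placebo split. With Week 24 for all, they fall in parent AV-101 subjects (Groups 1 and 2). With the randomization value for all, they fall in parent placebo subjects (Groups 3 and 4). That would be unequal ascertainment between the groups being compared, and a repeat walk that was not done in its window cannot be created at database lock.

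**Working it through.** The plan states no event rate, power or sample size for clinical worsening, so there is no figure to reproduce. The check compares the two possible thresholds.

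**Thresholds.** Let R be the parent randomization 6MWD and W the parent Week 24 6MWD. A repeat is due at or below 0.85 × R for a parent AV-101 subject, and at or below 0.85 × W for a parent placebo subject. At or below the lower threshold a repeat is due under either arm; above the higher one it is due under neither. Only between them is the site undecided, and that zone is 0.85 × |W − R| wide. If W = R there is no zone.

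**Illustrative subjects.**

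| R (m) | W (m) | 0.85R | 0.85W | Zone (m) | Later walk (m) | Fall from R | Fall from W |
|---|---|---|---|---|---|---|---|
| 350 | 320 | 297.5 | 272 | 25.5 | 290 | 60/350 = 17.1% | 30/320 = 9.4% |
| 350 | 380 | 297.5 | 323 | 25.5 | 310 | 40/350 = 11.4% | 70/380 = 18.4% |

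The first walk qualifies only if the subject was on AV-101; the second only if the subject was on placebo.

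**How often this could happen.** The documents give no 6MWD means or variances, so every input here is an assumption. Two sets were simulated, for the walk criterion at one later visit, without the FC III/IV condition.

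- Set A: baseline mean 360 m, SD 70; SD of change 40, 50 or 60 m per period; mean parent change 0, +20 or +35 m; mean later change −10 m.
- Set B: baseline mean 370 m, SD 80; SD of change 30, 50 or 70 m; mean parent change 0 to +40 m on active and 0 to −10 m on placebo; later change −10 or −30 m.

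| Result | Set A | Set B |
|---|---|---|
| Walks where the two thresholds disagree | 9–17% | 5–20% |
| Declines qualifying on R that a Week 24-for-all trigger misses | 30–50% | 17–58% |
| Declines qualifying on W that a randomization-for-all trigger misses | 23–52% | 14–23% |
| Qualifying declines missed by an either-value trigger | 0 | 0 |

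The last row is true by construction: repeating the walk at or below 0.85 × max(R, W) covers both thresholds.

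**Extra walks under an either-value trigger.** In Set A, compared with a Week 24-only trigger, about 3 to 12 per 100 walks. In Set B, compared with a trigger on the subject's true baseline, about 2 to 17 per 100.

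**Sections 6.6.5 and 8.5.2 side by side.** Section 6.6.5 makes confirmation compulsory. Section 8.5.2 item 4 counts the decline with no confirmation. If the first governs, an unrepeated decline is not an event. If the second governs, it is, and the confirmation rule does nothing in the analysis. On baseline, the general rule in Section 8.4 agrees with Section 6.6.5, but item 4 does not invoke it. Item 4 also counts events from the first parent dose, when a placebo subject's Week 24 value does not yet exist, so the reference value should be stated there.

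**The case against.** Several arguments limit this point, and most of them stand.

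- **The site is rarely helpless.** Both candidate values come from walks done in the parent study, and outside the zone the answer is the same under either arm. This stands. Within the zone, though, the text gives no rule, and checking both values is not something it asks for.
- **Confirmation is not permanently lost.** A reader might infer that missed events can never be recovered. The documents do not support that. Unscheduled visits are allowed at any time at the Investigator's judgment, and a sustained decline can trigger again at the next scheduled walk. What is lost is the confirmation for that episode. Because walks are 8 weeks apart between Weeks 4 and 12 and 12 weeks apart after that, a later trigger delays the event date. A subject who recovers or withdraws first may never be counted.
- **The blind is temporary.** A reader might extend the problem to all entrants. It is documented only for Phase 2b and Intermediate entrants before dose selection. Phase 3 entrants would be affected only if their parent arm stays undisclosed to the site, which the documents do not state.
- **Bias in the hazard ratios is not established.** The one-sided pattern requires sites to use a single fixed reference. Reliance on Week 24 is plausible because it is the extension's baseline visit, but no text says so. Mixed practice or precautionary repeats would not give that pattern. On the wording of Section 8.5.2, an unconfirmed decline would still count.
- **The simulated percentages are not percentages of clinical-worsening events.** They cover one of four components, at one visit, without the FC III/IV condition. This stands.
- **The synopsis says efficacy measures are collected only on the open-label optimal dose.** If that sentence governed, the blinded period would have no walks to judge. But Table 1 schedules the 6MWT from extension baseline without that limit, and Section 8.5.2 evaluates worsening throughout both studies. The passages need reconciling.

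**Conclusion.** The point holds for the blinded period before optimal-dose selection, for walks between 0.85 × the randomization value and 0.85 × the parent Week 24 value. There the site cannot apply the trigger as written. A confirmation can be missed for that episode, and the event delayed or lost, possibly unequally between parent AV-101 and parent placebo subjects. On assumed inputs the two thresholds disagree at about 5% to 20% of walks before the functional-class condition; no figure for events or hazard ratios can be derived from the documents. The direction and size of any bias depend on site behaviour that the documents do not describe. The conflict between Sections 6.6.5 and 8.5.2 on whether an unconfirmed decline counts needs no assumption.

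This should be fixed, but it does not undermine the study: the main objective is long-term safety, and the other three components of clinical worsening do not depend on the walk.

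**What to change.** 1. In the synopsis and Sections 2.2 and 6.6.5, separate the site's trigger from the endpoint definition. The site repeats the 6MWT on a different day within 2 weeks whenever 6MWD is at least 15% below either the parent randomization value or the parent Week 24 value, with the FC III/IV condition unchanged.
2. State that the allocation-specific baseline is applied at analysis, after unblinding. The endpoint itself does not change.
3. If the trigger is automated, base the flag on the either-value rule. A flag based on the subject's true baseline would reveal parent allocation whenever the walk falls in the zone between the thresholds.
4. In Section 8.5.2 item 4, state whether confirmation is required and which baseline applies, including for walks during the parent study.
5. Reconcile the synopsis sentence on when efficacy measures are collected with Table 1, and state when the parent arm of Phase 3 entrants is disclosed to sites.

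The cost is some extra repeat walks, about 3 to 12 per 100 walks compared with a Week 24-only trigger on the Set A assumptions, and fewer once the FC III/IV condition is applied. The repeat walk is already a protocol procedure. The wording change is short, but as an amendment it needs IRB/IEC approval (Section 9.3) across about 140 sites, so it is best combined with another amendment. It must be made prospectively, because missed repeats cannot be recreated afterwards.
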